4. SAMPLE SIZE JUSTIFICATION

The sample size for this Phase 2 study was chosen to estimate effect sizes and variability for a pivotal study. Assuming a standard deviation for change in VAS scores of 25, a mean change of 30 in the high dose group, 28 in the low dose group, and 10 in the placebo group, an Analysis of Variance (ANOVA) F-test at alpha of 5%, a sample size of 20:20:10 for high dose, low dose and placebo, respectively, will have 49% power to detect an overall difference among treatment groups.

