3.5.2. DISCONTINUED PATIENTS

Any patient may voluntarily discontinue the study at any time without prejudice. The investigator may discontinue a patient from the study at any time if (s)he considers that remaining in the study compromises the patient's health or the patient is not sufficiently cooperative. In either event, reason(s) for discontinuation should be recorded on the CRF.

Possible reasons for study discontinuation include the following:

- AEs necessitating discontinuation from the study (pre-treatment).
- The patient is lost to follow-up.
- Patient decision (specify).
- Investigator decision (specify).
- Other reason (specify).

The reasons for any patient discontinuation will be recorded on the study completion form of the CRF.

Discontinued patient(s) will be replaced in any treatment arm if discontinuation occurs prior to the 90 Day follow-up;

Patients discontinued for AE(s) will be followed-up after patient's discontinuation until the event is resolved or considered medically stable by the investigator.

Subjects that withdraw prior to study completion will undergo the following if possible:

- Retinal Fundoscopy
- Concomitant Medications
- Serum Chemistry and hematology
- Photograph and measurement of ulcer(s) if present at baseline
- Vital Signs
- Serum HGF if discontinued prior to Day 90
- Copies of VM202 in whole blood if discontinued prior to Day 90
- Injection site reaction assessment if discontinued prior to Day 49
- Adverse Events

In case of a patient lost-to-follow-up, the investigator must do his/her best to contact the patient (by phone or letter) at least twice. If no response is obtained from the patient, the investigator is encouraged to contact one of the patient's relatives or his/her general practitioner. The evidence of these contacts must be recorded in the patient medical chart. It can be, for instance, the acknowledgement of receipt of a letter sent to the patient.

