3. STUDY OVERVIEW

This is a 12 month Phase II, double-blind, randomized, placebo-controlled, multi-center study designed to assess the safety and efficacy of VM202 in subjects with critical limb ischemia.

Subjects who meet the eligibility criteria will be randomized in a 2:2:1 ratio to one of three treatment arms: Low Dose (8 mg VM202), High Dose (16 mg VM202) or placebo, respectively.

Subjects in the Low Dose Group (8 mg VM202) will receive:

- Day 0: 4 mg of VM202 (16 injections of 0.5 ml of VM202)
- Day 14: 4 mg of VM202 (16 injections of 0.5 ml of VM202)
- Day 28: Placebo only (16 injection of 0.5 ml normal saline)
- Day 42: Placebo only (16 injection of 0.5 ml normal saline)

Subjects in the High Dose Group (16 mg VM202) will receive:

- Day 0: 4 mg of VM202 (16 injections of 0.5 ml of VM202)
- Day 14: 4 mg of VM202 (16 injections of 0.5 ml of VM202)
- Day 28: 4 mg of VM202 (16 injections of 0.5 ml of VM202)
- Day 42: 4 mg of VM202 (16 injections of 0.5 ml of VM202)

Subjects in the placebo control group will receive 16 injections of 0.5 ml normal saline at each visit.

Table 1 lists the final dose and dose per visit to be administered by study arm.

Table 1. VM202 administration for each study arm

TREATMENT GROUP	FINAL DOSE VM202	DOSE VM202 (MG) PER VISIT			
		DAY 0	DAY 14	DAY 28	DAY 42
Low Dose	8 mg	4	4	0	0
High Dose	16 mg	4	4	4	4
Placebo	0	0	0	0	0

The schedule of study visits and the clinical parameters that will be measured at the visits are summarized in Table 2 below.

TABLE 2 SCHEDULE OF EVALUATIONS AND VISITS

PROCEDURE	Screening / Baseline (-30 – 0 D)	1 st Injection Day 0		2 nd Injection Day 14 ± 3 D		3 rd Injection Day 28 ± 3 D		4 th Injection Day 42 ± 3 D		Day 49 ± 3 D	Day 90 ± 7 D	6 mo ± 1 mo	9 mo ± 1 mo	12 mo ± 1 mo	Early Withdrawal
		Pre-dose	Post-dose	Pre-dose	Post-dose	Pre-dose	Post-dose	Pre-dose	Post-dose						
Baseline Evaluation															
Informed Consent	✓														
Complete Medical History	✓														
Complete Physical Exam	✓														
Cancer screening [†]	✓														
Viral screening – HIV, HTLV, HBV, HCV	✓														
Urinalysis	✓														
ECG	✓														
Pregnancy test	✓														
Safety and Efficacy Parameters															
Retinal Fundoscopy	✓													✓	✓
Vital Signs	✓	✓	✓	✓	✓	✓	✓	✓	✓	✓	✓	✓	✓	✓	✓
Concomitant Medications	✓	✓		✓	✓		✓	✓		✓	✓	✓	✓	✓	✓
Serum Chemistry and hematology	✓	✓		✓	✓		✓	✓		✓	✓	✓	✓	✓	✓
Photograph and measurement of ulcer(s) ^{††}	✓	✓		✓	✓		✓	✓		✓	✓	✓	✓	✓	✓

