6. ANALYSIS POPULATIONS

The following subject populations will be used for analysis:

The Intent-to-Treat (ITT) population will include all subjects who were randomized regardless of whether treatment was received. Subjects will be analyzed according to the treatment to which they were randomized.

The Safety population will include all subjects who receive at least one dose of study drug medication and data will be analyzed according to the treatment actually received. The safety analyses will be performed on the Safety population.

The per-protocol (PP) population will include all subjects who received the correct dose of study drug medication, have the 9-month VAS assessment, and do not have any protocol violations or major deviations as determined by Medical Monitoring. The per-protocol population will be determined in a blinded review before database lock. Subjects will be analyzed according to the treatment to which they were randomized. Primary efficacy analyses will be performed on the PP population.

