10. EFFICACY ANALYSES

The primary efficacy analysis will be based on the PP analysis population. Additional efficacy analyses will be performed on the ITT population.

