10.1. Primary Efficacy Variable

Subjects will be asked to assess the level of pain they feel by placing a perpendicular line on a scale of 0 (No Pain) to 100 (Pain as bad as it can be) at each visit. The subject's Visual Analogue Scale (VAS) score will be determined by where the subject places the perpendicular line by two independent readers. The average scores from the two readers will be used as the pain score for the corresponding subject. If a score is reported by only one reader, then that score will be assigned as the pain score. The primary efficacy endpoint is the change in pain level between baseline and the 9-month follow-up as determined by VAS. The change in pain will be calculated for each subject as follows:

$$\text{Change} = 9\text{-month VAS} - \text{Baseline VAS}$$

Since higher VAS indicates worse pain, a negative value of change means an improvement, and a positive value of change means deterioration.

The mean change in pain will be compared among the three treatment groups. The statistical null and alternative hypotheses for the primary efficacy endpoint are:

$$\begin{aligned} H_0: \mu_H &= \mu_L = \mu_P \text{ and} \\ H_a: \text{at least one of the three } \mu's &\text{ is different,} \end{aligned}$$

where μ_H , μ_L , and μ_P are mean change in pain from baseline to 9-month follow-up for VM202 high dose, VM202 low dose, and placebo groups, respectively.

One-way Analysis of Variance (ANOVA) with treatment (VM202 high dose, VM202 low dose, and placebo) as the factor will be used to compare the mean change in pain among the three treatment groups. Dunnett's test will be used to compare the mean change in pain level between VM202 high dose to placebo and between VM202 low dose to placebo. This analysis will be repeated using Percent (%) Change from Baseline, where Percent Change from Baseline is defined as:

- % Change from Baseline = [(9 month VAS – Baseline VAS)/Baseline VAS]* 100

An additional set of analyses will be run using non-parametric tests as described in Section 5.2 for continuous variables.

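### SAP section 4 states 49% power, but its printed inputs give 45% with 20:20:10 analysed, and no analysis population is named

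*SAP*

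**What the plan says.** SAP section 4 gives an estimation rationale first: "The sample size for this Phase 2 study was chosen to estimate effect sizes and variability for a pivotal study". It then lists the power inputs, beginning "Assuming a standard deviation for change in VAS scores of 25", with mean changes of 30 (high dose), 28 (low dose) and 10 (placebo) and an ANOVA F-test at an alpha of 5%. It concludes that "a sample size of 20:20:10 for high dose, low dose and placebo, respectively, will have 49% power to detect an overall difference" among the groups. It mentions neither an analysis population nor an allowance for loss.

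Other sections bear on that statement:

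- **Allocation (SAP section 3):** "Subjects who meet the eligibility criteria will be randomized in a 2:2:1 ratio to one of three treatment arms". The Protocol synopsis puts the total at 50, so 20:20:10 is the planned randomised split.
- **Primary test (SAP section 10.1):** "One-way Analysis of Variance (ANOVA) with treatment (VM202 high dose, VM202 low dose, and placebo) as the factor will be used" to compare mean change in pain. This is the same test as in the power statement.
- **Primary population (SAP section 10):** "The primary efficacy analysis will be based on the PP analysis population". Under SAP section 6, that set holds patients who had the correct dose, "have the 9-month VAS assessment, and do not have any protocol violations or major deviations as determined by Medical Monitoring".
- **Replacement (Protocol section 3.5.2):** "Discontinued patient(s) will be replaced in any treatment arm if discontinuation occurs prior to the 90 Day follow-up". No provision is made for replacing later losses.

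**The concern.** Section 4 prints every quantity needed to compute the power of the overall F-test, so the 49% can be checked directly. It does not follow from the inputs as printed.

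The second matter is smaller. The calculation uses all 50 planned patients, whereas the primary analysis uses only those who qualify for the per-protocol set. A reader could take the stated power to be that of the primary analysis. It would be so only if every patient, after replacement, met the per-protocol criteria.

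Little in this trial depends on the figure. What is at stake is the accuracy of a printed number in a section that looks ahead to a pivotal study. If the cause is the handling of unequal arms, the same method would misstate power again wherever arms are unequal.

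**Working it through.** **Inputs (SAP section 4):** SD 25; means 30, 28, 10; n = 20, 20, 10 (N = 50); overall F-test, alpha 0.05, on 2 and 50 − 3 = 47 degrees of freedom.

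**Power from the printed inputs**

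1. Weighted grand mean = (20×30 + 20×28 + 10×10)/50 = 1260/50 = 25.2.
2. Between-group sum of squares = Σ nᵢ(μᵢ − 25.2)² = 20×4.8² + 20×2.8² + 10×15.2² = 460.8 + 156.8 + 2310.4 = 2928.
3. Noncentrality λ = 2928/25² = 2928/625 = 4.685.
4. Critical value F(0.95; 2, 47) = 3.195.
5. Power = P[F′(2, 47; λ = 4.685) > 3.195] = 0.451. A simulation of 300,000 trials gives 0.452.

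The stated 49% is therefore not reproduced. The difference is 49 − 45.1 = 3.9 percentage points.

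**What does give about 49%**

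- *Unweighted grand mean.* Mean of 30, 28 and 10 = 22.67. Then 20×7.333² + 20×5.333² + 10×12.667² = 1075.6 + 568.9 + 1604.4 = 3248.9; λ = 3248.9/625 = 5.198; power 49.3%. Every printed input is unchanged, but this is not the noncentrality of the F-test when the groups are unequal.
- *Rounded inputs.* Moving one input by half a unit in the favourable direction is not enough: 46.4% (high dose 30.5), 45.9% (low dose 28.5), 47.1% (placebo 9.5), 46.7% (SD 24.5). Moving several together can be: 48.8% (placebo 9.5 with SD 24.5) and 49.2% (30.5/28.5/9.5 with SD 25).
- *Large-sample chi-square approximation.* 47.7%. This is closer, but it is not the stated F-test.

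**Other readings of the same inputs**

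| Calculation | Power |
|---|---|
| Equal allocation of 50 | 58.9% |
| Alpha 0.10 | 58.4% |
| High dose vs placebo, two-sided t (28 df) | 51.4% |
| Low dose vs placebo, two-sided t (28 df) | 43.5% |
| Dunnett, at least one dose | 52.2% |

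None of these is the stated calculation, and none gives 49%.

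**Scale.** With the weighted mean and the printed inputs, 22:22:11 analysed (55 patients) gives λ = 5.153 and 49.2%. This only shows how large the gap is; it is not a proposal to enrol more.

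**Effect of per-protocol losses.** The documents give no expected rate. The table assumes, for illustration, the same proportional loss in each arm.

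| Assumed loss | Analysed | λ | F df | Power |
|---|---|---|---|---|
| 0% | 20:20:10 | 4.685 | 2, 47 | 45.1% |
| 10% | 18:18:9 | 4.216 | 2, 42 | 40.9% |
| 20% | 16:16:8 | 3.748 | 2, 37 | 36.5% |
| 30% | 14:14:7 | 3.279 | 2, 32 | 32.0% |

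**The case against.** The strongest reply is that nothing turns on the figure. Section 4 opens with an estimation purpose, the Protocol's statistical section makes no power claim, and both 45% and 49% are below one half. That is a fair account of the consequences and limits the point to a minor correction. It does not make the printed number right.

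A second reply is that the inputs are whole numbers and may have been rounded. This stands in part: 49% lies within the rounding interval. It requires at least two inputs to have been rounded in the same favourable direction, however, and the SAP does not say that unrounded values were used. The failure to reproduce is a statement about the inputs as printed.

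Third, the unweighted-mean explanation is conjecture about how the figure was produced. That is correct. It is offered as one possible source, and the discrepancy does not depend on it.

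Fourth, power conditional on 20:20:10 is a complete statement in itself and does not promise a per-protocol set of that size. Early discontinuations are replaced, and SAP section 10.1.2 imputes VAS so that all ITT patients are included. Neither mechanism covers losses from Day 90 onward or per-protocol exclusions in the primary analysis, so the observation holds. It is a clarification rather than an error, and secondary to the arithmetic. The loss rates shown are assumptions and must be labelled as such wherever they appear.

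**Conclusion.** The concern holds. On the printed inputs, the overall F-test with 20:20:10 analysed has 45.1% power, not 49%, an overstatement of 3.9 percentage points. This rests on reading the inputs exactly as printed, a common SD of 25, normally distributed changes and the F-test that section 4 names. The documents do not reveal where 49% came from.

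The 45.1% applies to 50 analysed patients. For the per-protocol primary analysis it is an upper figure unless replacements keep the set at 20:20:10. How much lower the power would be cannot be stated without an expected loss rate; the illustrated range is 40.9% to 32.0% for assumed losses of 10% to 30%.

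The practical weight is small, but the figure is wrong as written and cheap to correct.

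**What to change.** In SAP section 4, restate the power as about 45% with 20:20:10 analysable patients. Alter the printed means or SD only if the sponsor's records show that unrounded values produced 49%; in that case print those values.

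Add one sentence saying that the figure refers to 50 analysed patients, whereas the primary analysis is on the per-protocol population, where losses that are not replaced reduce it. If examples help, give the 10%, 20% and 30% results and mark them as illustrations under an assumed equal proportional loss per arm.

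The cost is one corrected number and one added sentence. Design, enrolment and analysis stay as they are.

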5. GENERAL ANALYSIS CONSIDERATIONS

The statistical analyses will be reported using summary tables, figures, and data listings. Continuous variables will be summarized with means, standard deviations, standard error, medians, minimums, and maximums for each treatment arm. Categorical variables will be summarized by counts and by percentage of subjects in corresponding categories.

All analyses and tabulations will be performed using SAS[®] Version 9.1 or higher on a PC platform. Tables and listings will be presented in RTF format.

5.1. Visit Windows

Data at each scheduled follow up visit will be analyzed according to the nominal visit identified on the CRF, regardless of the actual elapsed time since treatment.

5.2. Statistical Methods

Two-sided p -values < 0.05 will be considered statistically significant, unless otherwise stated.

Separate statistical tests will be performed at each time point for key endpoints of interest.

In general, an overall test to determine if there is a statistically significant difference among the three treatment arms will be conducted first. Further comparisons will be made to determine if either the low or high dose groups are significantly different from the placebo group.

For continuous variables, a one-way analysis of variance (ANOVA) with treatment group (high dose, low dose, and placebo) as a factor will be used to determine if there is a significant difference among the groups. The low and high dose groups will each be compared against the placebo group using Dunnett's test. The mean difference between the VM202 groups versus placebo along with 95% confidence intervals for the mean difference will also be presented. To be viewed as secondary, an additional set of analyses will be run using non-parametric tests. A Jonckheere-Tepstra test will be applied to the VAS change from baseline results to detect overall trend differences. Non-parametric pairwise treatment comparisons versus placebo will also be made using Wilcoxon Rank Sum test. Within each treatment group for each endpoint, both a paired t-test (parametric) and Wilcoxon Signed Rank test will be run to test for differences comparing baseline to each post-baseline assessment.

For categorical variables, Fisher's exact test will be used to determine if there is a significant difference among the three treatment groups. Separate Fisher's exact tests will be used to compare the low and high dose groups to the placebo group.

For time-to-event variables (such as amputation, limb salvage and mortality), Kaplan-Meier estimates will be used to estimate survival times. Differences in survival times will be compared among groups using the log-rank test.

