6.2. STUDY ENDPOINTS

6.2.1. PRIMARY ENDPOINT

The primary study endpoint is to assess the difference in pain level between baseline and the 9 month follow-up as determined by VAS. Active and placebo arms will be compared to determine treatment effect. The primary analysis will be conducted in the efficacy analysis dataset. A secondary analysis will be conducted in the ITT analysis dataset, and further analyses conducted as necessary to explore any inconsistency between the two results.

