10.4. Multiplicity Adjustments

Pairwise comparisons using Dunnett's test adjust for multiple comparisons. Otherwise, there will be no adjustments for multiple comparisons or interim analyses.

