Safety Population

Intervention	Placebo (N=)	VM202- 8 mg (N=)	VM202- 16 mg (N=)
PTA	n (%)	n (%)	n (%)
Peripheral bypass	n (%)	n (%)	n (%)
Amputation above the knee	n (%)	n (%)	n (%)
Amputation below the knee	n (%)	n (%)	n (%)
Atherectomy	n (%)	n (%)	n (%)
Surgical bypass	n (%)	n (%)	n (%)
Endarterectomy	n (%)	n (%)	n (%)
Thrombectomy	n (%)	n (%)	n (%)
Stent placement	n (%)	n (%)	n (%)
Other	n (%)	n (%)	n (%)

path\t_program.sas date time

Table 5.1.1
Visual Analogue Scale for Pain (mm)
Per-Protocol Population

	----- Placebo (N=) -----		--- VM202- 8 mg (N=) ---		--- VM202- 16 mg (N=) --	
	Result	Change ^[2]	Result	Change ^[2]	Result	Change ^[2]
Baseline ^[1]						
N		n		n		n
Mean (SD)		xx.x (xx.xx)		xx.x (xx.xx)		xx.x (xx.xx)
Median		xx.x		xx.x		xx.x
Min, Max		xx, xx		xx, xx		xx, xx
Day 14						
N		n		n		n
Mean (SD)		xx.x (xx.xx)		xx.x (xx.xx)		xx.x (xx.xx)
Median		xx.x		xx.x		xx.x
Min, Max		xx, xx		xx, xx		xx, xx
Comparison vs. Placebo						
Model 1 ^[3]						
LS Means (SE)			xx.x (xx.x)		xx.x (xx.x)	
LS Mean Differences (SE)				xx.x (xx)		xx.x (xx)
95% CI for LS Mean Differences				(xx.x, x.xx)		(xx.x, x.xx)
Overall p -value for Treatment Differences						x.XXXX
Pairwise p -value vs. Placebo (Dunnett's test)				x.XXXX		x.XXXX
Baseline vs. Day 14 (Paired t-test)			x.XXXX	x.XXXX		x.XXXX
Model 2 ^[4]						
Overall p -value for Treatment Differences (Jonckherre-Terpstra test)						x.XXXX
Pairwise p -value vs. Placebo (Wilcoxon Rank Sum test)				x.XXXX		x.XXXX
Baseline vs. Day 14 (Wilcoxon Signed Rank test)			x.XXXX	x.XXXX		x.XXXX

^[1] Baseline defined as the last non-missing value prior to first dose of study drug.

^[2] Change = Change from Baseline

^[3] One-way analysis of variance (ANOVA) with treatment groups as a factor.

^[4] Nonparametric tests for differences across a one-way classification of treatment.

path\t_program.sas date time

Programmer Note Repeat for all available time points, Day14, Day 28, Day 42, Day 90, 6mo, 9mo, and 12mo.

Programmer Note Tables 5.1.2 will be identical to Table 5.1.1 for the ITT Population using imputation rules specified in Section 10.1.2 of the Statistical Analysis Plan.

Table 5.2.1
Visual Analogue Scale for Pain- Percent (%) Change from Baseline
Per-Protocol Population

	Placebo (N=) Change ^[2]	VM202- 8 mg (N=) Change ^[2]	VM202- 16 mg (N=) Change ^[2]
Day 14- Percent (%) Change from Baseline ^[1]			
N	n	n	n
Mean (SD)	xx.x (xx.xx)	xx.x (xx.xx)	xx.x (xx.xx)
Median	xx.x	xx.x	xx.x

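### The SAP's primary hypothesis and its only power figure belong to the three-arm F-test, while the protocol asks active versus placebo; the Dunnett comparisons already planned should be named as primary

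*SAP*

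**What the plan says.** Protocol 6.2.1 frames the primary endpoint, change in VAS pain from baseline to 9 months, as a comparison with placebo: "Active and placebo arms will be compared to determine treatment effect".

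SAP 10.1 writes the primary null as equality of the high-dose, low-dose and placebo means, with the alternative that at least one differs, and tests it by one-way ANOVA. It then adds the comparisons with placebo: "Dunnett's test will be used to compare the mean change in pain level between VM202 high dose to placebo", and likewise for the low dose. SAP 5.2 gives the order: "an overall test to determine if there is a statistically significant difference among the three treatment arms will be conducted first". The dose comparisons follow, with no condition that the overall test be significant. Every p-value is read at the same threshold: "values < 0.05 will be considered statistically significant, unless otherwise stated".

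SAP 10.4 covers multiplicity: "Pairwise comparisons using Dunnett's test adjust for multiple comparisons". It makes no other adjustment.

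SAP 4 gives power only for the overall test, an "Analysis of Variance (ANOVA) F-test at alpha of 5"%, and puts it at 49%.

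The shell for Table 5.1.1 (SAP Appendix B) prints the overall p-value, the two Dunnett p-values and a row labelled "95% CI for LS Mean Differences" under one model. Neither the shell nor section 5.2 says whether those intervals are Dunnett-adjusted.

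**The concern.** The hypothesis tested is wider than the question asked. A difference between low and high dose alone satisfies the SAP's alternative, so a significant F-test need not mean that either dose differs from placebo. The test that does answer the protocol's question is in the plan, but it sits behind an overall test that it does not need.

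Two further points are left open. The SAP does not say how the F-test and Dunnett's test relate: gate, co-primary, or one primary and one supportive. It also does not say which kind of interval stands beside the Dunnett p-values. At stake are a clear primary result, a power figure for the test that matters, and a primary table whose intervals and p-values cannot disagree.

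**Working it through.** **Inputs.** All are from SAP 4 and 5.2: arms of 20 (high), 20 (low) and 10 (placebo); mean changes 30, 28 and 10; "standard deviation for change in VAS scores of 25"; two-sided 5%. The means are read as mm on the 0–100 scale of SAP 10.1. Their sign does not affect the result. Error degrees of freedom: 50 − 3 = 47.

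**The SAP's own figure.**
- Weighted mean: (20×30 + 20×28 + 10×10)/50 = 25.2.
- Noncentrality: [20×4.8² + 20×2.8² + 10×15.2²]/25² = (460.8 + 156.8 + 2310.4)/625 = 4.685.
- Critical F(2, 47) = 3.195. The noncentral F gives power of **45.1%**, not 49%. The large-sample chi-square approximation gives 47.7%, but that is not the F-test the SAP names.

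**Dunnett's test.** Both comparisons share the placebo arm, so their correlation is 20/(20 + 10) = 2/3. With 47 degrees of freedom the two-sided critical value is 2.253.

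**F and Dunnett together.** Results come from simulating arm means and pooled variance, with 10 million trials under the null and 4 million per alternative:

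| True means (high/low/placebo) | F | Dunnett, at least one dose | Either | Both (F as gate) | F only |
|---|---|---|---|---|---|
| All equal | 5.0% | 5.0% | 6.5% | 3.5% | 1.5% |
| 30/28/10 (SAP) | 45.1% | 52.3% | 52.8% | 44.6% | 0.6% |
| 30/10/10 | 66.9% | 44.6% | 68.4% | 43.1% | 23.7% |
| 20/0/10 | 58.4% | 23.9% | 59.0% | 23.3% | 35.2% |

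In the second row, Dunnett's power for each dose is 43.2% (high) and 35.5% (low). Adding F as a second route gains 0.6 points there. Making it a gate loses 7.7 points (52.3% to 44.6%).

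**Intervals.** The standard error of a dose-minus-placebo difference is 25×√(1/20 + 1/10) = 9.68.
- Unadjusted half-width: 2.012 × 9.68 = 19.5 mm.
- Dunnett half-width: 2.253 × 9.68 = 21.8 mm.
- Ratio: 2.253/2.012 = 1.12.

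If the printed intervals were unadjusted, then at the SAP's means about 17% of trials would show at least one dose whose interval excludes zero while its Dunnett p-value is 0.05 or more.

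**Per-protocol losses.** The primary population is per-protocol and SAP 4 allows for no loss. Assuming 10% to 20% loss (18:18:9 to 16:16:8), F-test power falls to 40.9% and 36.5%.

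**The case against.** **The SAP already identifies F as primary.** Section 10.1 states the null for it, section 4 sizes on it, and section 5.2 puts it first. This stands as the most natural reading, and on it the primary error is 5%. A reader might infer from the missing gate that the plan inflates its false-positive rate to 6.5%. The documents do not support that. The figure needs a rule that a significant result on either test counts as success, and the SAP states no such rule. Claims for a given dose taken from Dunnett alone stay at 5% across both doses.

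**F is not a weaker test in general.** This is correct. Its 45% falls short only of Dunnett's chance of finding at least one dose at the planned means. It exceeds Dunnett's power for either single dose (43% and 35%), and it is clearly stronger if only the high dose works (67% against 45%).

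**Rejection because the doses differ is remote.** SAP 3 gives both active arms the same injections on Day 0 and Day 14, and SAP 4 expects a difference of 2 mm. At those means F rejects without Dunnett in 0.6% of trials. The 20/0/10 row shows what the F-test responds to; it is not a forecast. The tables also show both Dunnett p-values beside the overall one, so a reader could see the source.

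**The interval type is unstated, not wrong.** A reader might infer that the intervals are unadjusted, but the interval sentence in SAP 5.2 directly follows the Dunnett sentence and may mean adjusted intervals. The 17% is therefore conditional.

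**The stakes are modest.** This is a 50-patient phase II trial sized to estimate effects. Its SAP lists safety as the primary objective, and other unadjusted analyses remain. That limits the importance of the point, but it does not make the stated hypothesis match the protocol's question.

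**Conclusion.** The mismatch holds. The protocol asks about active treatment against placebo; the SAP's primary hypothesis and power figure concern any difference among three arms. The planned Dunnett test answers the protocol's question and controls error by itself.

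At the sponsor's assumptions, naming it as primary gives about 52% power for at least one dose, against 45% for F, with error at 5.0%. That gain of about 7 points rests on both doses working about equally well, on SD 25 and on no losses. It reverses if only one dose works.

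The documents leave open whether F was meant as a gate, which would give 3.5% error under the global null and 44.6% power for at least one dose. They also leave open the type of interval. Neither silence shows an error in the plan, but both should be closed. This is a cheap improvement, not a defect that invalidates the primary analysis.

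**What to change.** - **SAP 10.1:** name the two Dunnett-adjusted comparisons with placebo as the primary analysis, restate the hypotheses to match, and label the F-test descriptive. Align the order given in 5.2, and say that Dunnett's test does not depend on the F result.
- **SAP 5.2 and the Appendix B shells:** state that the 95% intervals beside the Dunnett p-values are Dunnett simultaneous intervals.
- **SAP 4:** state power for that test: about 52% for at least one dose, 43% for the high dose and 35% for the low dose, before per-protocol losses. Correct or explain the 49% if the F-test figure is kept.

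The tests are already planned and no new data are needed, so the cost is SAP wording. There are two downsides. Intervals are about 12% wider than unadjusted ones (21.8 mm against 19.5 mm half-width), and power is lower than with F if only one dose works.
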